8.2.1 Criteria and Guidelines for Reportable Events

For the purposes of this clinical trial, the following events will be reported to the Sponsor for the duration of the trial:

- All hospital admissions, including:
 - All SAEs occurring during a hospital admission outside of the original indication for admission (e.g. stroke, myocardial infarction, etc.)
- Emergency department/hospital outpatient observation visits that are cardiovascular in nature
- All deaths
- HFHs that occurred within 12 months prior to baseline
- SAEs, ADEs, SADEs, and UADEs

Of the reportable events, the following events will be adjudicated by an independent CEC:

- Events that could contribute to primary endpoints for either trial arm, to determine which events meet primary endpoint qualification, including:
 - All cardiovascular hospitalizations, cardiovascular emergency department visits, and cardiovascular hospital outpatient visits, all defined as a hospital visit with the primary cause being cardiovascular in nature, as reported by the Investigator
 - All deaths
 - Any other hospitalizations which, when reviewed by the Sponsor, could potentially meet endpoint qualification
- HFHs that occurred within 12 months prior to baseline
- All events that could contribute to the secondary safety endpoint for either trial arm including ADEs, SADEs, and UADEs

A list of anticipated AEs is included in sections 7.1.1 and 7.1.2. The Sponsor will ensure that all applicable events are reported to the relevant authorities as per regulations. The sites should notify the Sponsor of reportable AEs by creating and saving the applicable CRFs within the electronic data capture (EDC) system. The description of the AE, date of the AE, treatment and resolution of the AEs will be reported, as applicable, to the relevant authorities per regulations. Additional information may be requested, when

required, by the Sponsor in order to support the reporting or adjudication of AEs. The Investigator must notify the IRB/EC, if appropriate, in accordance with national and local laws and regulations, of the AEs reported to the Sponsor.

8.2.2 Criteria and Guidelines for Non-Reportable Events

The following events are **not reportable** to the Sponsor:

- Non-serious AEs unrelated to the investigational device/procedure, including those occurring during the course of a hospitalization that are not the primary reason for the hospitalization
- Non-cardiovascular or trauma events unrelated to HF, not resulting in a hospital admission
- Minor outpatient non-cardiovascular procedures, such as colonoscopy or cataract surgery

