4.3.1.2 Secondary Endpoints

The secondary effectiveness endpoints are:

- Composite of recurrent HFHs or emergency department/hospital outpatient observation visits for intravenous diuretic therapy
- Health status at baseline, 6, and 12 months post-implantation as assessed by the EuroQol 5-Dimension, 5-Level (EQ-5D-5L) Questionnaire

- Health status at baseline, 6, and 12 months post-implantation as assessed by the Kansas City Cardiomyopathy Questionnaire (KCCQ-12)
- Six Minute Hall Walk (6MHW) test at baseline, 6, and 12 months post-implantation
- In addition, the individual components of the primary endpoint will each be evaluated as descriptive secondary effectiveness endpoints:
 - HFHs at 12 months post-implantation
 - Emergency department/hospital outpatient observation visits for intravenous diuretic therapy at 12 months post-implantation
 - All-cause mortality at 12 months post-implantation

The secondary safety endpoint is freedom from device/system related complications (DSRCs) at 12 months post-implantation. The secondary safety endpoint will be evaluated for all subjects enrolled in the Randomized Arm (i.e. with an attempted implant, whether successful or unsuccessful) and reported for the entire subject cohort and by subject group.

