5.5 Unscheduled Visits

Clinicians may follow standard of care for frequency of follow-up outside of the trial required visits. Routine office visits which are not required by the protocol, do not require reporting. However, all

[REDACTED]

[REDACTED]

reportable events (e.g., SAEs, ADEs, SADEs, UADEs, and non-AE device issues, see section 8.2) identified during an unscheduled visit are required to be reported and documented by completing the applicable CRF. Medication changes will be captured as they occur on the applicable CRF. For Randomized Arm subjects, the CardioMEMS™ Hospital Electronic Unit cannot be used during follow-up visits and PA pressure data can only be viewed on the Merlin.net™ website.

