 - An inpatient or prolonged hospitalization OR
 - A medical or surgical intervention to prevent life-threatening illness or injury or permanent impairment to a body structure or a body function OR
 - Fetal distress, fetal death or a congenital abnormality or birth defect

Note: A planned hospitalization for a pre-existing condition, or a procedure required by the CIP is not considered an SAE.

- **Adverse Device Effect (ADE):** An AE related to the use of an investigational medical device. This definition includes AEs resulting from insufficient or inadequate instructions for use, deployment, implantation, installation, or operation, or any malfunction of the investigational medical device. This definition includes any event resulting from the use error or from intentional misuse of the investigational medical device.
- **Serious Adverse Device Effect (SADE):** ADE that has resulted in any of the consequences characteristic of a serious AE.
- **Unanticipated Adverse Device Effect (UADE):** As defined in 21 CFR §812.3, any serious adverse effect on health or safety or any life-threatening problem or death caused by, or associated with, a device, if that effect, problem, or death was not previously identified in nature, severity, or degree of incidence in the CIP or application (including a supplementary plan or application), or any other unanticipated serious problem associated with a device that relates to the rights, safety, or welfare of subjects.
- **Non-AE Device Issue:** any instance when the device fails to perform or does not function properly without an associated an adverse clinical outcome.
- **Device/System Related Complication (DSRC):** An AE that is related or possibly related to the system (CardioMEMS™ PA Sensor or other components of the CardioMEMS™ HF System) and has at least one of the following characteristics:
 - is treated with invasive means (other than intramuscular medication or a right heart catheterization which is used for diagnostic purposes)
 - resulted in the death of the subject
 - resulted in the explant of the device

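### Randomized Arm: non-serious harms of reading-guided titration managed in the office or by telephone are likely to be captured unequally between Treatment and Control

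*Protocol*

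**What the plan says.** All Randomized Arm subjects are implanted and upload readings. Only Treatment is managed on those readings, and site staff cannot see them for Control (Protocol 4.1.2, 5.4.7). The arm is single-blind.

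Protocol 8.2.1 lists what must be reported. It opens with "All hospital admissions, including" SAEs that arise during an admission outside its original indication. It adds "Emergency department/hospital outpatient observation visits that are cardiovascular in nature", deaths, and "SAEs, ADEs, SADEs, and UADEs". Protocol 8.2.2 then removes "Non-serious AEs unrelated to the investigational device/procedure", including those arising during a hospitalization without being its main reason.

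Appendix C defines an ADE as "An AE related to the use of an investigational medical device" and extends this to implantation, operation and malfunction. Protocol 7.1.2 names dizziness and raised serum creatinine among possible ADEs/SADEs, without restriction by group.

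SAP 6.2 summarises ADEs, SADEs, UADEs and cardiovascular SAEs. It has no visible row for non-serious events irrespective of attribution.

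**The concern.** What differs between the groups is acting on the readings. The harms specific to that are harms of medication titration, such as symptomatic hypotension or dizziness. A randomized comparison of them needs the same ascertainment in both groups. Here, for events that stay outside hospital, ascertainment passes through a relatedness judgment made by someone who knows the allocation.

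The distortion can go either way. If investigators link such events to the use of readings, Treatment shows an apparent excess even when true risk is equal. If they attribute them to the drug, a true excess goes largely unreported. The trial is meant to support an expanded indication (Protocol 1 and 6.3), so a fair account of these harms has value even though they are not serious.

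**Working it through.** The plan states no figure on this point, so there is nothing to reproduce. The check is a reading of the rules, followed by an illustration on assumed inputs.

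**Routes by which a non-serious titration harm can be reported (Protocol 8.2.1, 8.2.2, Appendix C)**

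| Route | Relatedness test | Open to Control? |
|---|---|---|
| Hospital admission | None | Yes; but inpatient hospitalization is itself an SAE criterion, so this route mostly carries serious events |
| Cardiovascular emergency or observation visit | None | Yes |
| ADE | Related to use of the device | Formally yes; for a titration harm the link is hard to draw when no sensor reading guided the change |
| None of these (office or telephone) | – | Not reportable in either group |

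Office- and telephone-managed events therefore depend on the ADE route. Protocol 5.5 adds that routine office visits outside the protocol need no reporting unless a reportable event is identified. The CEC is to be blinded where possible (5.10.4), but it sees only what has already been reported, so it cannot recover an event filtered out at the site.

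**Illustration**

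- n = 500 per group (Protocol 4.1.2).
- p = true risk of a non-serious titration harm, equal in both groups. Assumed 10%.
- e = share of such events reaching an admission or cardiovascular emergency/observation visit, equal in both groups. Assumed 5% or 20%.
- a = share of the remainder that the investigator links to the device in Treatment. Assumed 10%, 25% or 50%; in Control assumed 0.

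Expected reports: Treatment = n·p·[e + (1 − e)·a]; Control = n·p·e. Here n·p = 500 × 0.10 = 50.

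| e | a | Treatment | Control | Ratio |
|---|---|---|---|---|
| 5% | 10% | 50 × (0.05 + 0.095) = 7.25 | 2.5 | 2.9 |
| 5% | 25% | 50 × (0.05 + 0.2375) = 14.4 | 2.5 | 5.75 |
| 5% | 50% | 50 × (0.05 + 0.475) = 26.25 | 2.5 | 10.5 |
| 20% | 10% | 50 × (0.20 + 0.08) = 14 | 10 | 1.4 |
| 20% | 25% | 50 × (0.20 + 0.20) = 20 | 10 | 2.0 |
| 20% | 50% | 50 × (0.20 + 0.40) = 30 | 10 | 3.0 |

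The ratio does not depend on p. Counts halve at p = 5% and double at p = 20%.

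If Control attribution is not zero, the gap narrows. With e = 5%, 25% attribution in Treatment and 5% in Control, Control becomes 50 × (0.05 + 0.95 × 0.05) = 4.9, and the ratio is 14.4/4.9 = 2.9.

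**Opposite direction.** Let no event be attributed in either group, with true risks of 15% v 10%, that is 75 v 50 subjects. Reports are 75e v 50e: 3.75 v 2.5 at e = 5%, and 15 v 10 at e = 20%. A true difference of 25 subjects shows as 1.25 or 5.

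These are counts of reports reaching the sponsor. A non-serious emergency visit not called an ADE would be among them but has no visible row in SAP 6.2. No significance test is attached, because the visible plan specifies none for these events.

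**The case against.** A reader might infer that titration harms can never be captured in Control. The documents do not support that. Admissions, cardiovascular emergency or observation visits, and SAEs are reportable in both groups without a relatedness test. Control subjects also carry the implant, and the ADE definition covers implantation and operation. A Control count of zero would need e = 0 and no attribution at all, which no rule imposes.

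A reader might also infer that the device/system related complication endpoint is distorted, since it covers "An AE that is related or possibly related to the system" and is "reported for the entire subject cohort and by subject group". That is not shown. Appendix C ties the term to the sensor or other system components, SAP 5.1.2.6 to the sensor or external electronics. Over-diuresis after a drug change is not naturally such an event in either group. The CEC also adjudicates these events.

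The list in Protocol 7.1.2 is weak evidence. It does not identify dizziness or raised creatinine as titration effects, and hypotension and volume depletion appear in neither 7.1.1 nor 7.1.2.

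Other data could show part of a true excess. Under Protocol 5.5, "Medication changes will be captured as they occur on the applicable CRF", and this applies to both groups. Creatinine/eGFR is measured at baseline, 6 and 12 months; hospitalizations, mortality and health status are also collected. None of these counts hypotension or dizziness as events.

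Redaction matters too. The telephone-contact rules (5.4.10), the contact worksheet (Appendix M) and the SAP section on medication changes are not readable, and the case report forms are not supplied. Further collection rules, including a recorded reason for each medication change, may exist.

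Finally, limited collection of non-serious unrelated events is a defensible choice for a marketed device. That stands as an argument against full AE collection, but not against a short list collected equally in both groups.

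**Conclusion.** The point holds in a limited form. In the Randomized Arm, a non-serious event that reaches neither an admission nor a cardiovascular emergency/observation visit is reportable only on a device- or procedure-relatedness judgment by an investigator who knows the allocation. Titration harms managed in the office or by telephone are therefore likely to be under-captured in Control relative to Treatment, or missed in both groups if attributed to the drug. The ADE counts in SAP 6.2 cannot support an unbiased between-group comparison of these harms.

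The size is unknown. With equal true risk and no attribution in Control, the apparent Treatment excess runs from 1.4-fold to 10.5-fold over the ranges shown. Every event rate, attribution share and visit share behind those figures is an assumption.

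The primary endpoint and the visible hypothesis tests are not affected. SAP 6.2 does not visibly promise a Treatment-versus-Control comparison, so the issue is the interpretation of harms by group. It is worth correcting because the correction is cheap.

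**What to change.** For the Randomized Arm, and for data collection only:

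- In Protocol 8.2.1 and 8.2.2, make a short prespecified list of non-serious events of interest (for example symptomatic hypotension and dizziness) reportable in both groups regardless of judged relatedness.
- Elicit them by the same method in both groups, at the existing scripted contacts and the 6 and 12 month visits. Contacts already occur at least every two weeks for three months and at least monthly thereafter (Protocol 4.1.2), and Table 2 already provides for AE reporting at them.
- In SAP 6.2, tabulate these events by randomized group irrespective of attribution. State that ADE counts by group are not a Treatment-versus-Control comparison of titration harms.

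The cost is modest extra site reporting for about 1000 subjects and one additional SAP table. No visit is added and clinical management does not change.

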7.1.1 Anticipated AEs

Events associated with the CardioMEMS™ PA Sensor or the implant procedure (in conjunction with RHC) or post-implantation complications are considered anticipated and include the following:

- Infection
 - Upper respiratory infection
 - Bronchitis
 - Pneumonia
 - Acute Bronchitis
 - Groin abscess
 - Methicillin-resistant staphylococcal aureus infection
 - Pulmonary Infiltration
 - Sepsis
- Arrhythmias
 - Ventricular tachycardia
 - Atrial fibrillation
 - Ventricular arrhythmia
 - Ventricular fibrillation
 - Atrial fibrillation with rapid ventricular response
 - Atrial flutter
 - Cardiac dysrhythmias
 - Tachycardia
 - Wide complex tachycardia

- Bleeding
 - Epistaxis
 - Hemoptysis
 - GI bleed
 - Bleeding
 - Blood in stool
 - Catheter site bleeding
 - Catheter site ecchymosis
 - Hematuria
 - Nose bleeds
- Hematoma
 - Hematoma
 - Catheter site hematoma
 - Vessel puncture site hematoma
- Thrombus
 - Arterial thrombosis (limbs)
 - Blood clot
- Myocardial infarction
- Transient ischemic attack
- Stroke
- Death
- Sensor embolization
- Pulmonary artery perforation

Refer to the CardioMEMS™ PA Sensor and Delivery Catheter, Model CM2000 User Manual for more information. If there are any questions regarding whether an event meets the associated definition (see Appendix C), the in-house Sponsor contact should be consulted.

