8.2 Safety Reporting

Safety surveillance and the safety reporting by the Investigator starts as soon as the subject is enrolled (all entry criteria are met, informed consent is provided, and implantation of the CardioMEMS™ PA Sensor is attempted) in either the Randomized Arm or the Single Arm.

Safety surveillance and safety reporting will continue until the last investigational visit has been performed, the subject is deceased, the subject's participation in the clinical trial is concluded by the Investigator, or the subject withdraws from the clinical trial.

All reportable (per section 8.2.1) AE data including deaths will be collected throughout the clinical trial and will be reported to the Sponsor on the applicable CRFs.

Reportable AEs will be monitored until they are adequately resolved or the subject has ended his/her participation in the trial, whichever comes first. The status of the subject's condition will be documented at each visit.

See *Appendix C* for event definitions regarding safety reporting.

SAE Reporting

The investigator should report all SAEs to the Sponsor as soon as possible but no later than outlined below.

Clinical Site	Reporting timelines
All Sites	SAEs must be reported to the Sponsor no later than 3 calendar days from the day the site personnel became aware of the event or as per the investigative site's local requirements, if the requirement is more stringent than those outlined.

The date the site staff became aware the event met the criteria of an SAE must be recorded in the source document. The Investigator will further report the SAE to the local IRB/EC according to the institution's IRB/EC reporting requirements.

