Appendix C: Definitions

- **NYHA HF Classification:** The NYHA HF Classification provides a simple way of classifying the extent of HF. It places subjects in one of four categories, based on how much they are limited during physical activity:
 - **Class I.** Patients with HF, but without resulting limitations of physical activity. Ordinary physical activity does not cause undue fatigue, palpitation, or dyspnea.
 - **Class II.** Patients with HF resulting in slight limitation of physical activity. They are comfortable at rest. Ordinary physical activity results in fatigue, palpitation, or dyspnea.
 - **Class III.** Patients with HF resulting in marked limitation of physical activity. They are comfortable at rest. Less than ordinary physical activity causes fatigue, palpitation, or dyspnea.
 - **Class IV.** Patients with HF resulting in inability to carry on any physical activity without discomfort. Symptoms of cardiac insufficiency, anginal syndrome, and dyspnea may be present even at rest. If any physical activity is undertaken, shortness of breath is increased.
- **Hospitalization:** Admission to hospital for at least 24 hours.
- **HFH:** A hospitalization determined to be due to ADHF as the primary cause for the admission and requiring intravenous diuretics, as adjudicated by the CEC.
[REDACTED]

- **Emergency department/hospital outpatient observation visits for intravenous diuretic therapy:** An unscheduled or unplanned admission to the emergency department (including freestanding or satellite emergency departments), hospital outpatient observation visit, or hospital inpatient visit (< 24 hours) determined to be due to ADHF at the primary cause for admission (as described in the HFH definition) and requiring intravenous diuretics, as adjudicated by the CEC.
[REDACTED]
- **Adverse Event (AE):** Any untoward medical occurrence, unintended disease or injury, or untoward clinical signs (including abnormal laboratory findings) in subjects, users or other persons, whether or not related to the investigational medical device under clinical investigation. This definition includes events related to the investigational medical device or the comparator. This definition includes events related to the procedures involved.
- **Serious AE (SAE):** An AE that led to:
 - Death
 - A serious deterioration in the health of the subject, that either resulted in:
 - A life-threatening illness or injury OR
 - A permanent impairment to a body structure or a body function OR

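### The second bullet of CIP 8.2.2 has no seriousness or device-relatedness limit, so read literally it exempts some SAEs and device effects that 8.2, 8.2.1 and 8.2.4 require sites to report

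*Protocol*

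**What the plan says.** The reporting duties in the protocol are broad. Section 8.2 says: "The investigator should report all SAEs to the Sponsor as soon as possible but no later than outlined below", and sets the limit at 3 calendar days. Section 8.2.1 lists as reportable all hospital admissions, all deaths and "SAEs, ADEs, SADEs, and UADEs", with no exception for cause or place of treatment. Among visits without admission it names only "Emergency department/hospital outpatient observation visits that are cardiovascular in nature". Section 8.2.3 covers deaths again, and 8.2.4 requires any UADE to be reported within 3 calendar days.

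Section 8.2.2 then lists what is not reportable. Its first bullet is limited to "Non-serious AEs unrelated to the investigational device/procedure". Its second reads "Non-cardiovascular or trauma events unrelated to HF, not resulting in a hospital admission".

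In Appendix C an event can be serious without admission. Two of the routes are "A permanent impairment to a body structure or a body function OR" and "A medical or surgical intervention to prevent life-threatening illness or injury or permanent impairment to a body structure or a body function". An ADE needs only a relation to the device. A DSRC needs at least a possible relation to the system plus invasive treatment, death or explant. Neither definition requires admission or a cardiovascular cause.

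**The concern.** The second bullet of 8.2.2 filters on cause (non-cardiovascular or trauma, not due to HF) and on place (no admission). The duties in 8.2 and 8.2.1 filter on seriousness and on relation to the device. These criteria cut across each other, so some events are both reportable and not reportable. Being unrelated to HF does not make an event unrelated to the device.

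A site that relies on 8.2.2 could leave out an SAE or a device effect in good faith. Freedom from DSRCs is the secondary safety endpoint in both arms (4.3.1.2 and 4.3.2.2), and the DSMB may advise on system-related event rates (5.10.3). Both depend on what sites send in. A site could also be faulted under 8.1, which gives failure to report device-related AEs as an example of non-compliance that exposes subjects to unreasonable risk, for doing what 8.2.2 literally says.

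**Working it through.** No arithmetic applies: the plan gives no figure on this point and no rate of such events. The check is to take the literal conditions of the second bullet and look for events that meet them and also fall under a reporting duty. Every case below is non-cardiovascular or trauma, unrelated to HF, and without admission.

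1. **A serious event**, such as an injury treated in the emergency department that leaves permanent impairment. It is an SAE under Appendix C and reportable under 8.2 and 8.2.1. The second bullet of 8.2.2 exempts it. Conflict.
2. **A device effect**, such as a groin abscess judged related to the device and drained as an outpatient. It is an ADE and reportable under 8.2.1. If it is judged at least possibly related to the system, the invasive treatment also makes it a DSRC. The bullet exempts it. Conflict. A SADE of this kind is in the same position.
3. **A UADE.** It is reportable under 8.2.1 and 8.2.4. The bullet exempts it. Conflict.
4. **A death**, such as a traumatic death outside hospital. It is reportable under 8.2.1 and 8.2.3. The bullet exempts it on its wording, but the duty to report deaths is stated separately and plainly.
5. **A non-serious, unrelated event of a type listed in 7.1.1**, such as an ordinary upper respiratory infection. Nothing makes it reportable, and the first bullet of 8.2.2 exempts it as well. No conflict.

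Next, can the bullet be read as silently limited to non-serious, unrelated events? The first bullet already removes those. So limited, the second bullet would remove no further adverse event. Among adverse events, all that its literal wording adds is those that are serious or related to the device or procedure, which are the ones 8.2 and 8.2.1 require.

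Last, would something downstream recover an event omitted at the site?

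- The CEC list in 8.2.1 is drawn from the reportable events, and the sponsor's additional screen there and in 5.10.4 is for hospitalizations. An event without admission may reach neither.
- Section 5.4.11.1 asks sites at the 6 and 12 month visits to report SAEs, device effects and emergency department visits not yet reported, with no cardiovascular limit. This is a real backstop, but it can act months after the 3-day limit.
- Section 5.5 repeats the duty for reportable events found at unscheduled visits and refers back to 8.2. Section 5.9 collects 8.2.1 events at a final visit after withdrawal.

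**The case against.** The strongest reply is that the bullet does not stand alone. Section 8.2 ties reportability to 8.2.1 and asks for all SAEs. Sections 5.4.11.1, 5.5, 8.1, 8.2.3 and 8.2.4 call again for SAEs, device effects, UADEs or deaths. The bullet can also be read as the mirror of the 8.2.1 entry that limits visits without admission to cardiovascular ones. On that reading it is loose drafting, and a site would have to disregard several other instructions to lose an event. This stands in part: it makes under-reporting a risk and not a certainty. It does not remove the conflict, because no section is given precedence and a site coordinator cannot tell from the text which reading is meant.

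Three stronger readings are tempting, and the documents do not support them.

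- *That 7.1.1 is contradicted, or that any event of a listed type must be reported.* Section 7.1.1 says only that "Events associated with the CardioMEMS™ PA Sensor or the implant procedure (in conjunction with RHC) or post-implantation complications are considered anticipated". It sets no reporting duty, and 8.2.1 merely points to it. A GI bleed treated in the emergency department is reportable if it is serious or device-related, not because its type is listed.
- *That losses fall unequally and favor Treatment.* The rule is the same in both randomized groups. Only the Treatment Group is managed on uploaded PA pressures, so unequal loss is conceivable, but nothing in the documents shows it. A fall after hypotension caused by HF treatment is also a poor example, because it is not clearly unrelated to HF.
- *That a number of lost events can be stated.* The documents give neither a rate for such events nor the share that sites would omit. Multiplying an assumed rate by the planned enrollment would only measure the assumption.

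**Conclusion.** The concern holds as an internal inconsistency in the safety reporting rules. Read literally, the second bullet of 8.2.2 conflicts with 8.2, 8.2.1 and 8.2.4 for non-cardiovascular SAEs, ADEs, SADEs and UADEs without admission, and the protocol does not say which prevails.

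Its size cannot be put in numbers from the documents. The exposure lies in timely SAE notification and in ADE, SADE and DSRC capture for the secondary safety endpoint. SAP 6.2 summarizes SAEs only where they are cardiovascular, so a non-cardiovascular SAE that is not a device effect would be absent from that summary even if reported; for such events what is at stake is notification and oversight. No effect on sample size or on the effectiveness hypotheses is shown. Deaths count in the primary composite but are separately protected by 8.2.1 and 8.2.3.

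The conclusion assumes that a site might take the bullet at its word. It assumes nothing about how often such events occur.

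**What to change.** Amend the second bullet of 8.2.2 in two places: begin it with *Non-serious*, and after the reference to HF add that the event must also be *unrelated to the investigational device/procedure*. Then add one sentence to the section: *Nothing in 8.2.2 overrides the reporting duties in 8.2, 8.2.1, 8.2.3 or 8.2.4.* So amended, the bullet exempts no adverse event beyond those the first bullet already exempts.

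Two additions should be avoided. A clause keeping every event type listed in 7.1.1 or 7.1.2 reportable would pull in non-serious, unrelated nose bleeds and bronchitis, which the first bullet exempts, and so create a new contradiction. A clause about medication changes guided by PA pressure would apply essentially only to the Treatment Group and would make ascertainment unequal.

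The cost is two sentences in the protocol and possibly a few more safety entries. No new procedure or visit is needed.
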